**8.2.2.5 Action Taken**

The Investigator will report the action taken with IP as a result of an AE or SAE, as applicable (i.e. discontinuation, interruption, or reduction of IP, as appropriate), and report if concomitant and/or additional treatments were given for the event.

#### **8.2.2.6 Outcome**

The Investigator will report the outcome of the event for both AEs and SAEs. The Investigator is responsible for following all SAEs until the event has resolved or has stabilized.

### **8.3 Abnormal Laboratory Values**

An abnormal laboratory value is considered to be an AE if the abnormality:

- Results in discontinuation from the study.
- Requires treatment, modification/interruption of IP dose, or any other therapeutic intervention; or
- Is judged to be of significant clinical importance.

Regardless of severity grade, only laboratory abnormalities that fulfill a seriousness criterion need to be documented as an SAE.

If a laboratory abnormality is one component of a diagnosis or syndrome, then only the diagnosis or syndrome should be recorded on the AE page/screen of the e-CRF. If the abnormality was not a part of a diagnosis or syndrome, then the laboratory abnormality should be recorded as the AE. If possible, the laboratory abnormality should be recorded as a medical term and not as an abnormal laboratory result (e.g., record thrombocytopenia rather than decreased platelets).

### **8.4 Adverse Events of Special Interest**

Adverse events of special interest include known side effects of Ifenprodil. Nausea, dry mouth, loss of appetite, heartburn, diarrhea, constipation, headache, dizziness, allergic reactions, and heart palpitations are known to occur in between 0.1 – 5% of patients. Elevated ALT/AST levels have been observed in <1% of patients.

### **8.5 Pregnancy**

All pregnancies or suspected pregnancies occurring in either a female patient or partner of a male patient must be reported immediately. The IP should be discontinued, and the patient withdrawn from the trial.

The Investigator will follow the female patient until completion of the pregnancy and collect the outcome of the pregnancy (either normal or abnormal outcome).

If the outcome of the pregnancy was abnormal, the Investigator should report the abnormal outcome as an AE. If the abnormal outcome meets any of the serious criteria, it must be reported as an SAE within 24 hours of the Investigator's knowledge of the event. All neonatal deaths that occur within 28 days of birth should be reported, without regard to causality, as SAEs. In addition, any infant death after 28 days that the Investigator suspects is related to the in-utero exposure to the IP should also be reported within 24 hours of the Investigator's knowledge of the event.

### **8.6 Serious Adverse Events**

#### **8.6.1 SAE Definition**

An SAE is an adverse event at any dosage that:

- Results in death;
- Is life threatening (in the opinion of the Investigator, at the time of the event);
- Requires inpatient hospitalization or prolongation of existing hospitalization;
- Results in persistent or significant incapacity/disability;

- Is a congenital anomaly/birth defect; or
- Is an important medical event

Important medical events are defined as those that may not be immediately life-threatening or result in death or hospitalization but may jeopardize the patient or may require medical or surgical intervention to prevent one of the other outcomes listed in the above definition. Medical and scientific judgement should be exercised in deciding whether events qualify as medically important.

### **8.6.2 Reporting of Treatment Emergent SAEs**

In order to meet the requirements for expedited reporting of SAEs meeting specific requirements to applicable regulatory authorities and IRB/IEC, all SAEs, must be reported to the Sponsor within 24 hours from the time the site investigational team first become aware of the event using the appropriate method as outlined in the Safety Reporting Guidelines.

As further information regarding the SAE becomes available, such follow-up information should be documented on a new SAE report form, marked as a follow-up report, and reported using the appropriate method as outlined in the Safety Reporting Guidelines.

Withdrawal from the study in the event of an SAE and therapeutic measures taken shall be at the discretion of the Investigator. A full explanation for the discontinuation from the study should be made in the patient's medical records and in the eCRF.

A planned hospitalization will not be a requirement of SAE reporting.

The Investigator is required to ensure that the data on these forms is accurate and consistent.

This requirement applies to all SAEs (regardless of relationship to IP) that occur during the study (from the time the patient signs informed consent until 7 days after the last dose of IP) or any SAE made known to the Investigator at any time thereafter that is suspected of being related to IP.

The SAE report should provide a detailed description of the SAE and include a concise summary of hospital records and other relevant documents. If a patient died and an autopsy has been performed, copies of the autopsy report and death certificate are to be sent to the Investigator as soon as these become available.

Where required by local legislation, the Investigator is responsible for informing the IRB/IEC of the SAE and providing them with all relevant initial and follow-up information about the event. The Investigator must keep copies of all SAE information on file, including correspondence with the IRB/IEC.

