**Table 3 Schedule of Events**

Trial Activity	Screening/Baseline/ Enrolment visit	Daily until hospital discharge	End of treatment	Follow-up period	
Day	1	2-14	15	29	60
Allowed window for visit (±)	-1 a		2	2	3
Visit	1		2 b	3	4
Informed consent	•				
Inclusion/exclusion criteria including confirmation of COVID-19 diagnosis	•				
Confirmation SARS-CoV-2 h	•	•	•	•	
Pregnancy test	•				
Demographics/Medical History	•				
Physical Exam	•				
Vital signs c	•	•	•	•	
Clinical support data collection f	•	•	•	•	
Safety Laboratory Testing d	•	•	•	•	
Cytokine Markers k	•	•	•		
Child-Pugh Score i	•	•			
PaO 2 and PaO 2 /FiO 2 ratio j	•	•	•	•	
ECG	•				
Cough Severity (VAS) e	•	•	•	•	
Extent of Dyspnea (Likert Scale) e	•	•	•	•	
Adverse Events documented	•	•	•	•	•
Concomitant Medications	•	•	•	•	
Randomization	•				
Administer IP	•	•			
Vital Status					• g

a Screening/baseline may occur up to 24 hours prior to randomization

b Treatment can be given up to 14 days post randomization, or until hospital discharge, whichever comes first. If patient is discharged prior to Day 14, the next visit should be Visit 2.

c Includes blood pressure (measured after the patient has been in a seated position (if possible) for ≥3 minutes of rest), pulse, respiratory rate, body temperature, and SpO2. Body weight and height will be measured at the screening visit only.

d Baseline, Days 3, 5, 8, 11 if hospitalized, Day 15, Day 29

e Baseline, Days 2, 4, 8, and 14 if hospitalized, Day 15 (if not done Day 14), Day 29

f Includes NEW Score, on Baseline, Days 3, 5, 8, 11 if hospitalized, Day 15, Day 29

g Vital status (is patient alive)

h Baseline, Days 5 (or discharge, whichever comes first) and 15. Day 29 for subjects with viral RNA detected at Day 15.

Qualitative (mandatory) and Quantitative (if available) testing done all days.

i Baseline, Days 3, 5, 8, 11 if hospitalized

j Minimum complete baseline, Days 3, 5, 8, 11, 15 and 29. If PaO2 not able to be taken, SpO2 should be obtained using a forehead sensor. Fingertip probes may be used if forehead sensors are not available. Remain consistent with the method of testing for the patient over the course of the study.

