#### **7.4.12 Safety Evaluations**

Adverse events reporting, including clinically significant laboratory abnormalities, physical examinations and vital signs. AE event collection will be performed from signing of ICF, until end of study.

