## **8.2 Collection and Reporting of Adverse Events**

### **8.2.1 Collection of Treatment Emergent Adverse Events**

The Investigator must monitor the condition of the patient throughout the trial from signing the ICF until the last visit.

The sources of treatment emergent adverse events cover:

- The patient's response to questions about his/her health (a standard non-leading question such as "How have you been feeling since your last visit?" is asked at each visit).
- Symptoms spontaneously reported by the patient.

- Investigations and examinations where the findings are assessed by the Investigator to be clinically significant changes or abnormalities.
- Other information relating to the patient's health becoming known to the Investigator (e.g. hospitalisation).

When an TEAE/SAE occurs, it is the responsibility of the investigator to review all documentation (e.g., hospital progress notes, laboratory, and diagnostics reports) relative to the event. The investigator will then record all relevant information regarding an TEAE/SAE in the e-CRF. It is not acceptable for the investigator to send photocopies of the patient's medical records in lieu of completion of the TEAE/SAE e-CRF page.

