12.2 Adverse Events

All AE verbatim terms will be coded using the Medical Dictionary for Regulatory Activities (MedDRA) version 21. Chest X-ray resulting in AEs will also be reported. Treatment Emergent Adverse Events (TEAEs) are all events which start or worsen after the first dose of study drug up to and including the follow up period. If missing dates or time prevent a clear determination as to whether the AE is treatment emergent, the adverse event will be regarded TEAE. If a patient experienced the same adverse event multiple times, this will only be counted once for the purpose of counting the number of patients experiencing that adverse event. For the SOC arm, all AEs are considered TEAEs.

An overall summary of TEAEs for counts and percentages by treatment groups defined in [section 3.4](#) will be provided for the following items:

- Any TEAE
- Any Serious TEAE
- Any type of serious TEAE (Result in Death, Immediately Life-Threatening, Inpatient hospitalization or prolongation of existing hospitalization, Persistent or Significant Disability or Incapacity, Congenital abnormality or birth effect, Important Medical event may require medical intervention to prevent events above)
- Any TEAE grade (intensity) experienced (Mild [Grade 1] Moderate [Grade 2] Severe [Grade 3] Life-Threatening [Grade 4] Fatal [Grade 5])
- Worst TEAE grade (intensity) experienced (Mild [Grade 1] Moderate [Grade 2] Severe [Grade 3] Life-Threatening [Grade 4] Fatal [Grade 5])
- Action taken (None, Medication Given, Procedure/Intervention Needed, Other)
- Action taken for Ifenprodil (Dose discontinuation, Drug interrupted, Unknown, None, Not Applicable)
- Action taken for SOC (Dose discontinuation, Drug interrupted, Unknown, None, Not Applicable)
- Outcome of TEAE (Recovered/Resolved, Recovering/Resolving, Recovered/Resolved with Sequelae, Not recovered, Death, Unknown, Patient discontinued from study)

- Relationship to Ifenprodil/SOC (Reasonable Possibility, No Reasonable Possibility, Not Applicable)

The following table summaries (counts, percentages and number of events) will be presented by System Organ Class and Preferred Term by treatment arm (defined in [section 3.4](#)):

- Summary of TEAEs
- Summary of Serious TEAEs.
- Summary of TEAEs (grade 1 or 2).
- Summary of TEAE (grade of 3 or more)
- Summary of Ifenprodil related TEAEs (applicable to Arm A and B only)
- Summary of SOC related TEAEs (applicable to all treatment arms)

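### The SAE reporting window is tied to the last IP dose, so it is undefined for the SOC arm, and the SAP starts counting treatment-emergent events earlier in SOC than in the ifenprodil arms

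*Protocol*

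**What the plan says.** **Reporting to the sponsor.** Under Protocol 8.6.2, SAEs "must be reported to the Sponsor within 24 hours from the time the site investigational team first become aware of the event". For SAEs of any cause this duty runs "from the time the patient signs informed consent until 7 days after the last dose of IP", and the section presents that span as the study period for this purpose. Beyond it, the duty covers only "any SAE made known to the Investigator at any time thereafter that is suspected of being related to IP".

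**Dosing.** IP ends at hospital discharge or Day 14, whichever is earlier (Protocol 6.2). One of the three equally allocated Phase 2b arms receives SOC alone (Protocol 4.1).

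**Collection.** Separate rules apply, with no distinction by arm. Protocol 7.4.12: "AE event collection will be performed from signing of ICF, until end of study". Protocol 8.2.1: "The Investigator must monitor the condition of the patient throughout the trial from signing the ICF until the last visit". Table 3 of the protocol has AEs documented at Days 15, 29 and 60.

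**Classification.** SAP 12.2 defines treatment-emergent events as "all events which start or worsen after the first dose of study drug up to and including the follow up period", then adds an exception: "For the SOC arm, all AEs are considered TEAEs". A footnote to Table 3 allows screening up to 24 hours before randomisation.

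**The concern.** Safety against SOC is part of the primary objective (Protocol 3.1), and Phase 2b is open label to patients, investigators, sites and CRO staff (Protocol 4.4). A fair comparison needs the same rule in each arm for which events are reported and which are counted. Two rules fail that test.

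First, the end of the SAE reporting window depends on an event that SOC patients never have. Sites must supply their own reading, and they may not agree. In the ifenprodil arms the end follows the discharge date. After it, whether an SAE is reportable rests on a causality opinion from someone who knows the treatment. Protocol 4.7 sets no safety stopping rules, so oversight depends on review of AE and SAE data by the medical monitor and the DSMB.

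Second, an event between consent and first dose is treatment-emergent in SOC. In an ifenprodil arm it is not, unless it worsens after dosing.

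**Working it through.** The plan states no figure to reproduce here. The check is day arithmetic on the stated windows.

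**Step 1. SAE reporting window, ifenprodil arms.** End = day of last dose + 7. Days outside = 60 − end. Share of 60 days inside = end / 60. The last possible dose is on Day 14 (Protocol 6.2); the earlier days are examples of early discharge.

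| Last dose | Window ends | Days outside, to Day 60 | Share inside |
|---|---|---|---|
| Day 1 | 1 + 7 = Day 8 | 60 − 8 = 52 | 13% |
| Day 5 | 5 + 7 = Day 12 | 60 − 12 = 48 | 20% |
| Day 7 | 7 + 7 = Day 14 | 60 − 14 = 46 | 23% |
| Day 14 | 14 + 7 = Day 21 | 60 − 21 = 39 | 35% |

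For a patient discharged before Day 14, Table 3 says "If patient is discharged prior to Day 14, the next visit should be Visit 2", which is Day 15 ±2. Take a Day 5 discharge. An SAE on Day 10 that the site learns of at Visit 2 is still reportable, because it occurred inside the window. An SAE on Day 13 is not reportable under 8.6.2 unless it is suspected to be related to IP.

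**Step 2. The same rule in SOC.** There is no last dose, so no end can be computed. The closing clause cannot help, because an SOC patient has no exposure to IP. Three readings are possible:

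- *Whole study.* Counting from consent up to one day before Day 1, SOC is covered for about 60 + 1 = 61 days. The ifenprodil arms are covered for at most 21 + 1 = 22 days. The ratio is 61 / 22 ≈ 2.8, with SOC more fully reported.
- *No IP, so no window.* SOC has no reporting period, against at most 22 days in the ifenprodil arms. The imbalance reverses.
- *End-of-treatment visit plus 7 days.* 15 + 7 = Day 22, close to the ifenprodil maximum of Day 21 but later than the window of an ifenprodil patient discharged early.

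**Step 3. Collection and tabulation.** Protocol 7.4.12 and 8.2.1 run from consent to the end of the study or last visit in every arm. SAP 12.2 tabulates serious TEAEs through follow-up and does not use the 7-day limit. Planned collection therefore ends at the same point in all arms. The conflict is between these sections and 8.6.2: for an unrelated SAE on Day 30, the first two call for recording, while 8.6.2 requires no SAE report from an ifenprodil arm and gives no answer for SOC.

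**Step 4. TEAE start.** Protocol 7.3.1 places the first dose after randomisation and within 24 hours of the screening procedures. If consent falls inside that period:

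- Ifenprodil arms: first dose to Day 60, about 60 days.
- SOC: consent to Day 60, up to about 61 days.
- Excess: 1 / 60 ≈ 1.7%, or 1 / 63 ≈ 1.6% to 1 / 57 ≈ 1.8% across the ±3-day visit window.

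The documents give no AE rate for that day. Assuming a 1% to 10% chance of a new AE, 50 × 0.01 = 0.5 to 50 × 0.10 = 5 of 50 SOC patients would have an event counted as a TEAE that would not count in an ifenprodil arm unless it worsened after dosing.

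**The case against.** A reader might infer that serious events are collected over different periods in the arms and that ifenprodil will therefore look safer. The documents do not support this.

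- **Reporting is not collection.** Section 8.6.2 governs 24-hour reporting to the sponsor. AEs, serious ones included, are to be recorded in the e-CRF from consent to the end of the study in all arms, and the SAP tables draw on that period. Deaths are also covered evenly, by vital status at Day 60 (Protocol 7.3.5) and mortality by arm (SAP 11.9).
- **The direction is not fixed.** It reverses between the first two readings in Step 2. A figure for bias in SAE rates would need an assumed onset pattern, one chosen reading, and no e-CRF capture of later events. The last of these contradicts the protocol.
- **Early closure is not shown to be typical.** Table 2 expects 36 + 37 = 73% of SOC and 31.90 + 50.70 = 82.6% of treated patients out of hospital at Day 15. It does not say when they left. Discharge on Day 13 or 14 closes the window on Day 20 or 21.
- **Oversight is not shown to be blind to late events.** Nothing says that the medical monitor or DSMB sees only 24-hour reports. The Safety Reporting Guidelines cited in 8.6.2 are not among these documents and may say more.
- **The start effect is small.** It lasts about a day. Conditions found through screening go to medical history (Protocol 7.4.2), and expected disease progression is generally not an AE (Protocol 8.1).

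All of this stands, and it limits the point. It does not supply an end date for SOC, reconcile 8.6.2 with 7.4.12 and 8.2.1, or justify an arm-specific TEAE definition. SAP 11.1 calls the pilot phase essentially exploratory. That lowers the stakes but does not remove the contradiction.

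**Conclusion.** The point holds as a defect in the reporting duty and in classification.

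1. The all-cause SAE reporting window ends by Day 21 in the ifenprodil arms, leaving at least 39 of 60 days outside it, and has no defined end in SOC. The duty to report to the sponsor can differ by arm. Neither the size nor the direction of any effect on the SAE comparison can be determined from the documents.
2. The TEAE rule has a known direction: it can only add events to SOC. The added period is at most about one day in 61, if consent falls within the 24-hour screening period. The 0.5 to 5 patients in Step 4 rest on an assumed event rate.

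Both conclusions assume that SOC patients appear in the safety tables, as SAP 3.4 and 12.2 intend. Read literally, SAP 4.1.3 limits the Safety population to patients who received study drug. That is a separate matter to correct.

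Severity is moderate. The wording should be settled before safety is compared by arm, but the documents do not show unequal planned collection.

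**What to change.** **Protocol 8.6.2.** Replace the end point based on the last IP dose with one window for all three arms, tied to randomisation or a study day and reconciled with 7.4.12 and 8.2.1. For example: all SAEs regardless of relationship from consent to the Day 60 visit, and after that any SAE suspected to be related to IP. A shorter common window would also remove the arm difference, provided the protocol says how it relates to AE collection up to Day 60.

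**SAP 12.2.** Delete the sentence that makes all SOC events treatment-emergent. In every arm, count events that start or worsen after randomisation, through Day 60, and list earlier events separately. Align the TEAE definition in Protocol 8.1.1.

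**Cost.** One sentence in 8.6.2, one in SAP 12.2 and the matching definition. With the Day 60 window there will be somewhat more SAE forms between about Day 12 to 21 and Day 60. No visits are added, since AEs are already recorded at Day 60. Starting at randomisation also counts the few ifenprodil-arm events between randomisation and first dose, which is the price of a common start.

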### **8.7 Follow-up of Treatment Emergent Adverse Events and Serious Adverse Events**

During the trial, the Investigator must follow-up on each adverse event until it is resolved or until the medical condition of the patient is stable.

After the patient's last visit, the Investigator must follow-up on any adverse event classified as serious or considered to have a reasonable possible causality to the IP until it is resolved or until the medical condition of the patient is stable. The Sponsor's Safety Surveillance Contact will follow all SAEs with outcomes pending until the last subject enrolled has completed the study.

## **9. DATA HANDLING**

### **9.1 Data and Documents**

The Investigator must ensure that the records and documents pertaining to the conduct of the study and the distribution of the investigational product are complete, accurate, filed, and retained. Examples of source documents include: hospital records; clinic and office charts; laboratory notes; memoranda; patient's diaries or evaluation checklists; dispensing records; recorded data from automated instruments; copies or transcriptions certified after verification as being accurate copies; microfiche; x-ray film and reports; and records kept at the pharmacy, at the laboratories and at medico-technical departments involved in the clinical trial.

### **9.2 Electronic Case Record Form**

An e-CRF system provided by an independent third-party CRO will be used for data capture. The system is validated and access at all levels to the system is granted/revoked following the CRO's procedures, in accordance with regulatory and system requirements.

Data should be entered into the system timely after the patient has attended a visit or after the data become available, as applicable.

The Investigator will approve/authorise the e-CRF entries for each patient with an electronic signature which is equivalent to a handwritten signature.

The e-CRF system and the database will be hosted at the independent third party CRO. After the trial database is declared clean and released to the statistician, a final copy of the database will be stored at the Sponsor. The Investigator will also receive a copy of the trial site's final and locked data (including audit trail, electronic signature and queries) as write-protected PDF-files produced by the independent third party CRO. The PDF-files will be stored on an appropriate electronic storage device and will be provided to the Investigator before access to the e-CRF is revoked.

Errors occurring in the e-CRF will be corrected electronically. Such corrections/modifications will be automatically tracked by an audit trail detailing the date and time of the correction and the name of the person making the correction.

### **9.3 Data Management**

Data will be collected via e-CRF and entered into the clinical database per the CRO's standard operating procedures (SOPs). This data will be electronically verified through use of programmed edit checks specified by the clinical team. Discrepancies in the data will be brought to the attention of the clinical team, and investigational site personnel, if necessary. Resolutions to these issues will be reflected in the database. An audit trail within the system will track all changes made to the data.

